2.3 Rationale

This clinical trial of adjuvant therapy (immediate ventilatory support, or hypertonic saline) for Malawian children with CM is directed toward the supportive treatment of increased brain volume, and it avoids the pitfalls that have bedeviled previous trials because:

- The interventions target a mechanism recently recognized as being strongly associated with a fatal outcome, severely increased brain volume; this mechanism is self-limited in CM survivors, suggesting that supportive care or rescue therapy may be effective.

The clinical trial setting in Malawi has been transformed because, beginning in July 2017, mechanical ventilation became available in the new Paediatric Intensive Care Unit (PICU) at the Queen Elizabeth Central Hospital.

This introduces new ethical issues: mechanical ventilation cannot be withheld in patients who suffer a respiratory arrest, and ventilatory support may result in a cadre of survivors with severe neurological sequelae. Therefore, “treatment failure” (failure of the primary intervention) is defined differently in the different therapeutic arms. In Arms 2 and 3, in which participants are not randomized to immediate ventilatory support, any participants who suffer respiratory arrest and are placed on ventilators *or* who die *or* are brain dead will be classified as treatment failures. In Arm 1, the patients who are randomized to receive immediate ventilatory support, “treatment failure” is defined as brain death at any time, *or* death at 7 days, with ventilatory support withdrawn.

The hypothesis underlying this prospective, randomized clinical trial is that death in children with CM occurs when raised intracranial pressure from severely increased brain volume impairs the function of the medullary respiratory center and that interventions which reduce ICP or support ventilation will improve survival rates in CM patients.

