3.2 Study Outcome Measures

3.2.1 Primary Outcome Measures

Final outcomes will be determined within 7 days: treatment success or failure, where failure is a composite outcome of death, ventilatory rescue, and brain death. Final outcomes within 7 days in children who meet the standard WHO definition of cerebral malaria treatment success or failure, where failure is a composite outcome of death, ventilatory rescue, and brain death.

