 - Continuous monitoring of heart rate and rhythm from EKG, respiratory rate, and pulse oximetry via monitor, and blood pressure via arterial line or cuff. Signals will be archived for offline analyses aimed at identifying heart rate variability patterns over time associated with CM and with clinical improvement or decline in association with treatment.

- Electrolytes and acid-base balance 3-hourly during the first 24 hours and 6-hourly thereafter (in those randomized to hypertonic saline)
- PRW and PICU
 - 2-hourly assessments of vital signs (including temperature) and Blantyre Coma Score until BCS = 5 and temperature is $\leq 37.5^{\circ}\text{C}$ for 24 hours, then 6-hourly.
 - 6-hourly assessments of malaria parasitemia and hematocrit, until two consecutive parasitemia counts are negative.
 - 12-hourly neurological examinations,
 - Daily ophthalmoscopy while unconscious
 - Daily ONSD measurements (while unconscious)
 - Daily TCD examinations
 - Daily MRI examinations (while unconscious if participant is clinically stable for transportation to undergo neuroimaging)

The primary objective (treatment success or failure) will be determined within the first 7 days of hospitalization (Figure 8)

Secondary objectives (Figure 8)

1. The secondary objective involving neurological sequelae at 1, 6, and 12 months after randomization will be determined in survivors randomized in the clinical trial.
2. The secondary objective of identifying surrogate measures of increased brain volume will include participants in the clinical trial as well as study subjects who are screened but do not meet inclusion criteria for clinical trial enrollment e.g. their brain volume is not increased enough to qualify for enrollment in the trial and are therefore not randomized.
3. The secondary objective of assessing the safety of early intubation and mechanical ventilation will include participants in the clinical trial as well as study subjects with CM who are screened but do not meet inclusion criteria for clinical trial enrollment e.g. their brain volume is not increased enough to qualify for enrollment in the trial and are therefore not randomized.
4. TCD endpoints will be determined on all participants (see section 7.2.2.4)]

Choice of participant population and sample size considerations

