1. Arm 1: Usual care + immediate mechanical ventilatory support (VENT) for a maximum of 7 days, with ventilator withdrawal once brain volume has decreased (brain volume score ≤ 5) or the patient has improved clinically (modified Blantyre Coma Score ≥ 3) or the patient dies or meets criteria for severe irreversible neurologic failure.
2. Arm 2: Usual care + intravenous hypertonic saline (HPS) for a maximum of 7 days, withdrawn once brain volume has decreased (brain volume score ≤ 5) and the patient

has improved clinically (Blantyre Coma Score ≥ 3) or the patient dies or meets criteria for severe irreversible neurologic failure.

3. Arm 3: Usual care (UC); intravenous fluids, intravenous artesunate; antipyretics, anticonvulsants and blood transfusions as needed; nutritional support) for a maximum of 7 days, or until brain volume has decreased (brain volume score ≤ 5) and the patient has improved clinically (Blantyre Coma Score ≥ 3) or the patient dies or meets criteria for severe irreversible neurologic failures

Participants will remain in the study throughout their hospitalization and, in survivors, through the 12-month post-randomization follow-up visit. Children are discharged when two sequential 6-hourly blood films are free of malaria parasites, when they have been afebrile for 24 consecutive hours, and when they are able to take medications and food by mouth. Final data collection will be at 12 months post-randomization.

Stratification:

No stratification is required. The ages of retinopathy-positive CM with severely increased brain volume per MRI who survived were compared to those of participants from the same population that died. There was no difference in the age structure (data not shown, $p=0.95$).

Primary and secondary outcomes.

The primary outcome is treatment success or failure, determined within the first 7 days. Treatment success is recovery. Treatment failure is death, ventilatory rescue (for participants in Arms 2 and 3) or meeting criteria for severe irreversible neurologic failure.

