6.7 Dosage, Preparation and Administration of Study Intervention/Investigational Product (VENT)

Mechanical ventilation will be initiated immediately after randomization to Study Arm 1, or in the event of a respiratory arrest for subjects allocated to Arms 2 and 3.

Endotracheal intubation will be performed by a pediatric intensivist after administration of IV anesthetic agents in doses described in the sedation section (Section 6.3). The size of the endotracheal tube to be used for each patient will be determined by the pediatric intensivist on-site using standard formulas. A variety of sizes of both cuffed and uncuffed endotracheal tubes will be available (ranging from size 3.0 to 7.5) along with laryngoscopes and different sizes of blades

At the discretion of the intensivist, initial ventilator settings may be set to deliver a Tidal Volume at 6-8 ml/kg, age-appropriate respiratory rate, Peak End Expiratory Pressure of 5 and Fraction of Inspired Oxygen at 40%. The settings will be adjusted by the pediatric intensivists to target a pCO₂ (partial pressure of carbon dioxide) in arterial blood of 35-40 mmHg and maintain oxygen saturation above 90% on pulse oximetry.

At the discretion of an intensivist, an arterial line may be placed in the ventilated subjects to measure arterial blood gases every 3 hours for the first 24 hours and every 6 hours subsequently until the participant is extubated.

Participants will remain intubated until brain volume has decreased (brain volume score \leq 6) and the participant has improved clinically (modified Blantyre Coma Score \geq 3) or the patient has improved clinically (modified Blantyre Coma Score \geq 4, no repeat MRI needed) or the patient dies or develops severe irreversible neurologic damage or for a maximum of 7 days.

Intubated participants will be moved from side to side every 2 hours (\pm 1 hour) to reduce chances of bed sores. If tolerated, they will undergo endotracheal suctioning every 6 hours (\pm 2 hours) and more often as needed to prevent plugging of the endotracheal tube by mucoid secretions, using an appropriate sized suction catheter attached to wall suction. Participants may be pre-medicated prior to suctioning using sedation medications described in section 6.3.

Participants will receive chest physiotherapy as needed if they develop evidence of lung atelectasis. They may be premedicated with sedation medications as described in section 6.3.

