11.4 Outcomes

The primary endpoint is death within one week following randomization. In Arm 2 and Arm 3, the endpoint will include failure of the initial treatment allocation such that the patient requires rescue ventilation. Several secondary outcomes will be assessed in the trial. Table 8 gives a brief description and preferred analytic strategies. Additional details are provided elsewhere in the Protocol.

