11.5 Sample Size and Power

For the primary outcome death/failure of the intervention, we conduct two parallel studies: (i) VENT versus control UC, (ii) HPS versus control UC. Approximately 128 children will be enrolled in the studies. This includes the 64 children in UC comprised of 16 randomized to UC in the 2018-2019 malaria seasons and augmented by 48 historical controls from previous seasons (2014-2017). We also randomized 16 children to VENT in the 2018-2019 malaria seasons.

Table 8: Summary of outcome measures and analytic plan		
Outcome measure	Outcome type/scale	Analytic method
PRIMARY OUTCOME		
Success of primary intervention or survival in the first 7 days after randomization	Binary	Logistic regression
SECONDARY OUTCOMES		
Brain volume determination (MRI on admission, then daily)	Ordinal	Ordinal regression
Optic Nerve Sheath Diameter (on admission, then daily)	Continuous	Linear regression. Serial assessments by repeated measures analysis
Transcranial Doppler ultrasound (on admission, then daily)	Continuous	Linear regression. Serial assessments by repeated measures analysis
Opening CSF pressure (mm CSF) (on admission)	Continuous	Linear regression
Heart rate variability patterns	Continuous	Linear regression. Serial assessments by repeated measures analysis
Neurologic exam * (on admission, then twice daily)	21 binary and 5 continuous variables	Linear or logistic regression
Papilledema (on admission, then daily)	Binary	Logistic regression
Severe neurologic sequelae at 16 and 12 months	Binary	Logistic regression. Serial assessments by repeated measures analysis
Hypotension that occurs within 30 minutes of sedation administration, initiation of mechanical ventilation or ventilator pressure adjustment.	Binary	Logistic regression.

Since the beginning of this study, we faced several logistical challenges but had success in recruiting 32 children in 2018-2019 (16 each in VENT and UC). Based on our current data, the estimated mortality in UC and VENT are respectively, 36% and 25%. Maintaining the mortality rate in UC, a one-sample lower test at significance level $\alpha=0.05$ of a null difference has 80% power to detect a reduction in mortality to 18% in VENT with 33 subjects in VENT.

[figure not shown]

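### The primary endpoint is defined inconsistently: a ventilated-arm child alive but unrecovered at day 7 has no agreed class, and the 7-day window closes just as the 7-day ventilation maximum expires

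*Combined protocol and SAP*

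**What the plan says.** The Protocol Summary and Section 4 (Primary and secondary outcomes) set recovery against a list of failure events. In Section 4 the wording is "Treatment success is recovery. Treatment failure is death, ventilatory rescue (for participants in Arms 2 and 3) or meeting criteria for severe irreversible neurologic failure". Neither place says what recovery is.

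Section 3.2.1 says "failure is a composite outcome of death, ventilatory rescue, and brain death" and does not define success. Section 2.3 defines failure in Arm 1 as brain death at any time or "death at 7 days, with ventilatory support withdrawn".

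The statistical section differs. Section 11.4 says "The primary endpoint is death within one week following randomization" and adds rescue ventilation for Arms 2 and 3. Table 8 in Section 11.5 lists the primary outcome as "Success of primary intervention or survival in the first 7 days after randomization".

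On timing, the Protocol Summary, Section 11.4 and Table 8 count from randomisation, whereas a sentence in Section 4 says the primary objective "will be determined within the first 7 days of hospitalization". Section 6.7 starts ventilation in Arm 1 immediately after randomisation. It continues until improvement, or until the child dies, "develops severe irreversible neurologic damage or for a maximum of 7 days".

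**The concern.** One foreseeable day-7 state, alive but still comatose or on the ventilator, has no single class. Section 4 has study clinicians determine the primary outcome in an open-label trial, so an undefined class leaves room for a judgement that varies by arm.

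The timing adds a directional problem. For a child ventilated to the maximum, support ends as the endpoint window closes. Ventilation could then move a death past day 7 without preventing it, and that death would fall outside the primary endpoint. Under Section 11.4, rescue ventilation in the hypertonic saline and usual care arms is already a failure, so it cannot hide a later death there. Of the 64 usual care children, 48 are historical controls from 2014-2017. Section 2.3 dates ventilation at the hospital from July 2017, and Section 4 says the intensive care unit was still under construction that year. Deaths in those controls could essentially not have been postponed in this way.

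**Working it through.** **Step 1. The definitions side by side.** The last column follows a VENT child who is alive at day 7, still comatose or ventilated, and has no listed neurologic endpoint.

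| Place | Success | Neurologic failure term | Clock starts | This child |
|---|---|---|---|---|
| Protocol Summary | recovery (undefined) | brain death | randomisation | neither success nor listed failure |
| 2.3 (Arm 1) | not stated | brain death, at any time | not stated | no listed failure |
| 3.2.1 | not defined | brain death | not stated | no listed failure |
| 4, outcomes | recovery (undefined) | severe irreversible neurologic failure | hospitalisation, elsewhere in Section 4 | neither success nor listed failure |
| 11.4 | not stated | none | randomisation | non-event |
| Table 8 | success of intervention, or survival | none | randomisation | success |

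**Step 2. The two 7-day limits.** Ventilation starts at randomisation and ends by day 7 at the latest. The Section 11.4 window also runs from randomisation to day 7. For a child ventilated to the maximum, the time between the end of support and the end of the window is 7 − 7 = 0 days. If the clock started at hospitalisation, the window would close earlier still. Section 2.3 ties Arm 1 status to support having been withdrawn, but 3.2.1, 11.4 and Table 8 do not carry that through.

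**Step 3. Reproduce the plan's sample size.** Inputs from Section 11.6: p0 = 0.28, a 50% relative reduction so p1 = 0.14, one-sided alpha 0.05, power 80%.

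n = (1.645 + 0.842)² × 0.14 × 0.86 / 0.14² = 6.183 × 0.1204 / 0.0196 = 37.98, so 38, as stated.

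**Step 4. What one child is worth.** Section 4 projects 32 VENT children, against the 38 in Section 11.6. One child of 32 is 3.1 points, and 3.1/14 = 22% of the 14-point target. Two are 6.25 points, or 45%. The one-sided exact binomial probability P(X ≤ x) at p0 = 0.28 is:

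| VENT children | Events | p |
|---|---|---|
| 32 | 4 | 0.033 |
| 32 | 5 | 0.081 |
| 38 | 5 | 0.026 |
| 38 | 6 | 0.062 |

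These are fixed-sample tests, without the four-stage boundary.

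**Step 5. Sensitivity at the last reported look.** Section 11.6 reports 3 deaths in 19 and conditional power of 76.1% at the observed difference. I used a single final look at 38 and the variance at p1:

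CP = Φ[(−1.645√T − θT)/√(T − I)], with I = 19/0.1204 = 157.8 and T = 38/0.1204 = 315.6.

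- 3/19: θ = −0.122, CP = 77%, within about one point of the stated value.
- 4/19: θ = −0.069, CP = 28%.
- 5/19: θ = −0.017, CP = 3%.

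At θ = 0 the approximation gives 21.4% against the stated 18.6%, so it is a guide and not an exact replica. The 4/19 and 5/19 lines assume that one or two children change class. The documents do not report that this happened for the reason discussed here.

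**The case against.** The strongest reply is that the outcome is declared binary and only failure events are enumerated, so success can be read as their absence. That agrees with 11.4, and Table 8 can be taken as shorthand for it. This is a workable reading, but the plan does not state it, and the Protocol Summary and Section 4 say recovery instead. The two neurologic terms may be synonyms, and the hospitalisation clock is a single phrase. Both are then wording repairs, but they still need making.

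Several stronger inferences are tempting and are not supported:

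- *That some section calls the alive, unrecovered child a failure.* None does so explicitly. Section 4 does so only for the child who meets criteria for severe irreversible neurologic failure.
- *That deaths after ventilator withdrawal are missed in VENT.* Ventilation can end early on improvement, and deaths after withdrawal but by day 7 count. Only deaths after day 7 fall outside, and that cut-off also applies to a never-ventilated child in the other arms. Nor are later deaths lost to the trial: follow-up runs to 12 months (Section 4), and survival by arm is the primary safety parameter (Section 9.1).
- *That up to about 5 of 32 children could be affected,* from the statement in Section 2.3 that 85% have died or been discharged by 72 hours. Being in hospital is not being in coma, since discharge also requires clear films, no fever and oral intake. For the high-brain-volume subset, Section 2.3 says nearly all survivors are discharged within 72 hours. Neither figure comes from children ventilated under this protocol.
- *That the gap between 3/19 (Section 11.6) and 5/19 died or brain dead (Section 4) shows late deaths.* It is consistent with brain death being counted differently. It shows only how sensitive the result is to classification.

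**Conclusion.** The point holds in this form. The primary endpoint has incompatible definitions. An alive but unrecovered VENT child is unclassified in the Protocol Summary and Section 4 and a non-event in 11.4 and Table 8. The neurologic term and the clock also vary. A VENT child ventilated to or near the maximum who dies after day 7 is not a primary event. Any such postponement can favour only VENT, given the rescue rule in 11.4 and a control group that is 48/64 = 75% historical.

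The number of children affected is not in the documents and is probably small. The concern is material because the test is small: one reclassified child moves the VENT rate by 3.1 points at 32 children and can carry the exact p-value across 0.05. The documents do not show that any child has been misclassified so far.

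**What to change.** Reconcile the Protocol Summary and Sections 2.3, 3.2.1, 4, 11.4 and Table 8 into one endpoint definition. It should give every day-7 state a single class, use one neurologic term with its criteria cited, and count from randomisation. Apply it identically to all arms and to the derivation of the control rate. Record that the clarification was made after two looks at VENT mortality (2/16 and 3/19).

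Keep the primary endpoint and pre-specify two sensitivity analyses:

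1. Randomised children alive but still ventilated or comatose at day 7 are counted as failures. Section 8.1 already treats a Blantyre Coma Score of 2 or less as comatose and records the score every two hours until consciousness returns.
2. All-cause death through hospital discharge and through the 1-month visit, including historical controls only where those data exist. For the 48 historical controls, Section 4 shows baseline variables and death or survival, but no day-7 coma score, discharge date or 1-month status.

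For that reason, a new primary success rule based on coma score and ventilation status is not recommended. It would change the endpoint after open looks at the data and might not be computable for most of the controls.

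The cost is protocol and SAP wording plus a little extra analysis. The VENT estimate may come out slightly less favourable. No change to any ventilation or withdrawal rule is proposed.

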Centralization of evaluations: MRI, ophthalmoscopy, ONSD, TCD, EEG, and neuro-checks will be carried out either at the bedside in the PRW/PICU or in the MRI suite.

Safety monitoring: A local independent safety monitoring team (ISM) will be appointed for the study. The team will consist of two local physicians with knowledge of the clinical setting and practices, but without direct involvement with this study. They will be notified of all SAEs and asked to comment on the relatedness of these events to the interventions. They will also be asked to review AEs at the discretion of the local investigators, IRBs, or the Data Safety and Monitoring Board (DSMB).

A DSMB is justified for this study for two reasons: (1) the anticipated mortality in this group of gravely ill children, without adjunctive treatment, is over 30% (2), and serious adverse events have been reported for HPS (Section 2.3.1.2) and assisted ventilation (Section 2.3.1.3). Interventions may result in survival of children who would have otherwise died, and some of these children may be severely neurologically impaired. In a country like Malawi where there is no social support for such children and their families, their survival could create a burden for the family which might worsen stress and social problems.

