5.3.2 Masking Procedures

Treatment arms will not be masked.

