9.2.1.2 Relatedness

The relatedness of the AE will be assessed by a study clinician based on the temporal relationship of the AE and any interventions, as well as the likelihood of other causal etiologies of the specific AE.

Related – There is a reasonable possibility that the intervention caused the adverse event. Reasonable possibility means that there is evidence to suggest a causal relationship between the study product and the adverse event.

Not Related – There is not a reasonable possibility that the administration of the study product caused the event.

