9.2.3 Serious Adverse Events

An adverse event or suspected adverse reaction is considered "serious" if, in the view of either the investigator or sponsor, it results in any of the following outcomes:

- Death,
- A life-threatening adverse event,
- Hospitalization or prolongation of existing hospitalization,
- A persistent or significant incapacity or substantial disruption of the ability to conduct normal life functions, or
- A congenital anomaly/birth defect.

Important medical events that may not result in death, be life-threatening, or require hospitalizations may be considered serious when, based upon appropriate medical judgment they may jeopardize the participant and may require medical or surgical intervention to prevent one of the outcomes listed in this definition. Only events that are not attributable to the malarial illness, that are outlined in section 2.4.1.2, or that were unanticipated, but that are considered to be possibly related to the study intervention will be graded and reported as Adverse Events to the sponsor, IRBs, and independent safety monitors.

- Life-threatening adverse event: An adverse event is considered “life-threatening” if, in the view of either the investigator or sponsor, its occurrence places the participant or subject at immediate risk of death. It does not include an adverse event, had it occurred in a more severe form, might have caused death.

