9.2.3.1 Protocol defined SAEs

CM is a disease with a high mortality rate. Reported mortality rates range from 15 – 30%, with our site having a rate of 18% over the past 25 years. We anticipate the mortality rate in randomization arm 3 will be approximately 37%. All deaths not attributable to the malarial illness will be reported to independent safety monitors, IRBs, and the sponsor as required.

- Death not caused by respiratory arrest secondary to intracranial hypertension.
- Prolongation of existing hospitalization for more than 7 days due to an intervention.
- A life-threatening adverse event that is not part of the study outcomes defined in the study objectives, an attributable to an intervention.

9.2.4 Procedures to be Followed in the Event of Abnormal Laboratory Test Values or Abnormal Clinical Findings

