9.3 Reporting Procedures

9.3.1 Serious Adverse Events

The reporting period for SAEs will be between the time of randomization and the twelve month (± 2 weeks) post-randomization follow up visit.

SAE reporting will be carried out as follows

The study clinician will complete a Serious Adverse Event Form (Appendix D) and SAEs thought to be related to study related procedures will be reported within 24 hours of their recognition, to the independent safety monitor, the IRBs at Michigan State University and the University of Malawi College of Medicine, and the sponsor, unless advised otherwise by the DSMB.

Any AE that meets a protocol-defined serious criterion will be submitted on an SAE form to the DMID Pharmacovigilance Group, at the following address:

DMID Pharmacovigilance Group
Clinical Research Operations and Management Support (CROMS)
[name]
[name]
SAE Hot Line: [name] (US) or [name] (outside US)
SAE FAX [contact] (US) or [name] (outside US)
SAE Email Address: [contact]

Other supporting documentation of the event may be requested by the DMID Pharmacovigilance Group and will be provided as soon as possible.

The DMID medical monitor and clinical protocol manager will be notified of the SAE by the DMID Pharmacovigilance Group. The DMID medical monitor will review and assess the SAE for regulatory reporting and potential impact on study subject safety and protocol conduct.

At any time after completion of the study, if the investigator becomes aware of an SAE that is suspected to be related to study product, the investigator will report the event to the DMID Pharmacovigilance Group, the independent safety monitor, and the IRBs of the University of Malawi and Michigan State University.

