9.5 Halting Rules

The following eventuality would trigger temporary suspension of enrollment until a safety review is convened and further evaluation undertaken:

- Five subjects where current HPS regimen is unable to achieve the target Na⁺ levels of 150-160 mmol/L.
- Any SAE deemed to be related to each of the experimental medical interventions (ventilator support or infusion of 3% hypertonic saline solution).

DMID retains the authority to suspend additional enrollment and study interventions during the entire study, as applicable.

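### Section 4 promises the independent monitors all SAEs, but Section 9 filters by attribution first, and 9.5 does not say whose relatedness judgement halts enrolment

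*Combined protocol and SAP*

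**What the plan says.** Section 4, under safety monitoring, appoints two local physicians who know the setting "but without direct involvement with this study". It says of them: "They will be notified of all SAEs and asked to comment on the relatedness of these events to the interventions". It gives no time limit.

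Section 9 describes the flow of reports differently:

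- **9.2.1.2:** "The relatedness of the AE will be assessed by a study clinician". Section 5.3.2 adds: "Treatment arms will not be masked".
- **9.2.1:** an event that leads to death, admission or a longer stay is reported as an SAE only if it is on the hypertonic saline list in 2.4.1.2, or unanticipated, and thought possibly related. The same section says that every AE is to be documented whatever its relationship, but that is record-keeping, not notice to the monitors.
- **9.2.3:** seriousness is first defined by outcome, with death included. A reporting sentence follows that opens with the word only and ends: "considered to be possibly related to the study intervention will be graded and reported as Adverse Events to the sponsor, IRBs, and independent safety monitors".
- **9.2.3.1:** "All deaths not attributable to the malarial illness will be reported to independent safety monitors, IRBs, and the sponsor as required".
- **9.3.1:** "SAEs thought to be related to study related procedures will be reported within 24 hours of their recognition, to the independent safety monitor", and to the IRBs and the sponsor.
- **9.5:** enrolment is suspended for a safety review after "Any SAE deemed to be related to each of the experimental medical interventions". Nobody is named as the person who deems it so.

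**The concern.** Section 4 gives the relatedness question to people outside the study. Section 9 puts a study clinician's attribution ahead of them. In an open-label trial in comatose, critically ill children, many serious events could be put down either to malaria or to the intervention, and the clinician who chooses knows the arm. If the choice is malaria, Section 9 may not bring the event to the monitors in time for them to disagree.

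What is at stake is the halting rule. It fires on one event, and whether it fires turns on relatedness. A single not-related call can decide the matter where no other SAE has been deemed related.

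**Working it through.** The documents give no figure for this point to reproduce, so the check is a comparison of the sections.

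| Section | What reaches the monitors | Test applied first | Timing |
|---|---|---|---|
| 4 | All SAEs, for comment on relatedness | None | Not stated |
| 9.2.1 | Decides what is reported as an SAE | Listed or unanticipated, and possibly related | Not stated |
| 9.2.3 | Events passing the test | Attribution to malaria or to the intervention | Not stated |
| 9.2.3.1 | Deaths | Not attributable to malaria | As required |
| 9.3.1 | SAEs | Thought related to study procedures | 24 hours |
| 9.2.1.3 | Listed expected events, with the clinician's relatedness call | On the list | Monthly |

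**Step 1. Does 9.3.1 alone contradict Section 4?** No. It can be read as an expedited clock for related SAEs, with the others following later.

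**Step 2. Do the other sections allow that reading?** Not comfortably. Section 9.2.3 restricts what is reported to the monitors, not how fast. Section 9.2.3.1 does the same for deaths. The grammar of 9.2.1 and 9.2.3 leaves it unclear whether the relatedness test also applies to listed events, but on any reading some attribution test comes before the report. If an SAE is what the outcome-based definition in 9.2.3 says it is, Section 4 and these sections cannot both be followed.

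**Step 3. Does a narrower meaning of SAE resolve it?** If SAE in Section 4 means only events that have passed the filter, the texts agree. The monitors can then change related to not related, but have no stated occasion to change not related to related. The check would work only in the direction that weakens safety.

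**Step 4. A case built from the documents.** Section 2.4.1.2 lists rebound cerebral edema as a known effect of hypertonic saline. Section 2.1.13 holds that the disease itself kills through swelling, raised pressure and respiratory arrest. Rebound edema is not on the monthly list in 9.2.1.3, and the first protocol-defined SAE in 9.2.3.1 leaves out deaths by that route. If the clinician attributes such a death to malaria, Section 4 sends it to the monitors and no route in Section 9 does so for a relatedness judgement.

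**Step 5. The other routes.** The sponsor's medical monitor receives protocol-defined SAEs (9.3.1), but two of the three criteria in 9.2.3.1 already require attribution to an intervention. The DSMB sees data by arm each year (9.6) and may meet more often once halting rules are initiated.

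**Step 6. Scale for deaths (illustration).** The projected enrolment table in Section 4 gives 32 VENT and 32 HPS, so 64 children on an intervention. Take mortality from 14% (the hypothesised VENT rate in 11.6.1) to 36% (UC in 11.5), and assume that HPS lies in the same range:

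- 64 × 0.14 = 9.0
- 64 × 0.36 = 23.0

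About 9 to 23 deaths in the intervention arms would meet the malaria test in 9.2.3.1. How many would be put down to malaria is not given.

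**The case against.** The strongest reply is that oversight is thicker than the comparison suggests, and much of it stands:

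- Section 9.3.1 can be read as a timeline only.
- The monthly reports in 9.2.1.3 carry the clinician's relatedness call, so for listed events the monitors can see it and dispute it. Those are the complications most readily tied to saline or intubation.
- Section 9.2.4.1 makes serum sodium above 190 mmol/L an SAE with no relatedness judgement.
- Section 9.2.3.1 tests deaths for attribution to malaria, which is not the same as a not-related call on the intervention.
- Section 4 lets the local investigators, the IRBs or the DSMB refer AEs to the monitors.
- Section 9.1 makes survival by arm the primary safety parameter, and the DSMB reviews it whatever the attribution of each death.

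A reader might therefore be tempted by three stronger readings that the documents do not support:

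- **That the monitors never see an event called unrelated.** The routes above show otherwise.
- **That nobody independent would know.** The DSMB would see deaths by arm, though late and in aggregate.
- **That the halting rule rests on the clinician's view alone.** Section 9.5 names no decider, and Section 4 invites the monitors' comment, so their judgement may already count. Linking Section 4 to 9.5 is an inference, though a reasonable one: Section 4 is the only place that asks an independent party about relatedness.

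What the reply does not remove is the restriction in 9.2.1, 9.2.3 and 9.2.3.1. None of the backstops asks for an independent relatedness judgement on each SAE.

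**Conclusion.** The conflict is real and should be resolved. Section 4 promises a review of all SAEs; Section 9 filters by attribution before that review and gives 24-hour notice only to SAEs already thought related. The independent check is weakened, not removed. The weakness is greatest for serious events outside the monthly list and for deaths attributed to malaria. Separately, 9.5 has a one-event trigger with no named judge.

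The share of SAEs affected cannot be estimated, because the documents give no rate at which clinicians call events related. The 9 to 23 deaths above show only how many pass through one filter, under the stated mortality range.

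The conclusion assumes that staff follow Section 9 as the operating text, and that the DSMB charter and manual of procedures, which are not among the documents, do not already settle the matter. It is a gap in participant protection and does not by itself affect the validity of the efficacy comparison.

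**What to change.** 1. Reconcile 9.2.1, 9.2.3, 9.2.3.1 and 9.3.1 with Section 4. Every event that meets the outcome-based definition in 9.2.3, deaths included, goes to the independent monitors whatever the clinician's attribution. State the time limit. Changing 9.3.1 alone would leave the earlier filters in place.
2. Record the monitors' own relatedness judgement beside the clinician's on each SAE.
3. State in 9.5 whose relatedness judgement triggers the suspension, and include the monitors' judgement.
4. Use one term for what relatedness refers to: 9.3.1 speaks of procedures, while Section 4 and 9.5 speak of interventions.

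The cost is protocol wording and a few more forms for two monitors already provided for. It restores what Section 4 already commits to.
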